### **13.1.1. Days -7 to -1**

A second set of screening procedures may be performed between Days -7 to -1:

- Physical examination
- Determine ECOG performance status
- Obtain height and vital signs (blood pressure, heart rate, respiratory rate, temperature, and weight)
- ECG
- Pregnancy test (women of childbearing potential)
  - A serum or urine pregnancy test will be performed during Screening, as well as at least once per cycle prior to dosing or more frequently as clinically indicated, and at the End of Therapy (EOT) visit.
- CBC with differentials
- Serum chemistries to include sodium, potassium, magnesium, phosphate, total protein, chloride, bicarbonate, calcium, BUN, creatinine, uric acid, total bilirubin, alkaline phosphatase, AST, ALT, LDH, albumin, and glucose.
- Update concomitant medications

### **13.2. Treatment Period (Cycle 1 to End of Therapy Visit)**

Note: Physical exam, performance status, vital signs including weight, CBC w/differentials and serum chemistry labs may be performed up to 3 days prior to Day 1 of each cycle.

Pregnancy tests (serum or urine) will be performed for women of childbearing potential at least once per cycle prior to dosing, or more frequently as clinically indicated, as well as during Screening and at the EOT visit.

#### **13.2.1. Cycle 1**

##### **13.2.1.1. Cycle 1, Day 1**

The following procedures will be performed on Cycle 1, Day 1:

- Physical examination
  - Note: The Cycle 1, Day 1 physical examination is not required if the Screening physical examination was conducted within 3 days prior to administration of the first dose of study drug (Cycle 1, Day 1).
- Update ECOG performance status
- Vital signs (blood pressure, heart rate, respiratory rate, temperature, and weight)
- Lymphoma assessment (includes physical examination, a review of the subject's current signs and symptoms, B symptoms, and concomitant medications)
- CBC with differentials

- Serum chemistries (sodium, potassium, magnesium, phosphate, total protein, chloride, bicarbonate, calcium, BUN, creatinine, uric acid, total bilirubin, alkaline phosphatase, AST, ALT, LDH, albumin, and glucose)
- Pregnancy test (women of childbearing potential)
- Collect plasma for PK sampling (2 hours post-dose)
  - CUDC-907 will be administered in the clinic on PK sampling days
- Update concomitant medications
- Collect AEs
- CUDC-907 dosing (CUDC-907 is taken PO for 5 days on/2 days off)

**13.2.1.2. Cycle 1, Days 2-4, Days 8-11, Days 16-19**

- CUDC-907 dosing (CUDC-907 is taken PO for 5 days on/2 days off)

**13.2.1.3. Cycle 1, Days 5 and 12**

The following procedures will be performed on Cycle 1, Days 5 and 12:

- Symptom-directed physical examination
- Vital signs (blood pressure, heart rate, respiratory rate, temperature, and weight)
- CBC with differentials
- Serum chemistries (sodium, potassium, magnesium, phosphate, total protein, chloride, bicarbonate, calcium, BUN, creatinine, uric acid, total bilirubin, alkaline phosphatase, AST, ALT, LDH, albumin, and glucose)
- Update concomitant medications
- Collect AEs
- CUDC-907 dosing (CUDC-907 is taken PO for 5 days on/2 days off)

**13.2.1.4. Cycle 1, Day 8**

- Collect plasma for PK sampling (2 hours post-dose, for first 50 subjects enrolled on amendment 4)
  - CUDC-907 will be administered in the clinic on PK sampling days

**13.2.1.5. Cycle 1, Day 15**

The following procedures will be performed on Cycle 1, Day 15:

- Optional tissue collection for biomarker sampling (from subjects with accessible tumor lesion) may be obtained within 8 hours post-dose on any dosing day from Cycle 1, Day 15 through Cycle 2, Day 1.
  - CUDC-907 will be administered in the clinic on tissue sampling days

- Update concomitant medications
- Collect AEs
- Collect plasma for PK sampling (2 hours post-dose, for first 50 subjects enrolled on amendment 4)
- CUDC-907 dosing (CUDC-907 is taken PO for 5 days on/2 days off)

### **13.2.2. Cycles 2 through 6**

#### **13.2.2.1. Cycles 2 through 6, Day 1**

The following procedures will be performed on Day 1 of Cycles 2 through 6:

- Physical examination
- Update ECOG performance status
- Vital signs (blood pressure, heart rate, respiratory rate, temperature, and weight)
- Lymphoma assessment (includes physical examination, a review of the subject's current signs and symptoms, B symptoms, and concomitant medications)
- Radiologic assessment (CT/MRI are required at the end of Cycle 2 ( $\pm$  3 days), Cycle 4 ( $\pm$  3 days) and Cycle 6 ( $\pm$  3 days). If FDG-PET/CT is acquired at baseline, follow-up FDG-PET/CT imaging at Cycle 4 is required)
- CBC with differentials
- Serum chemistries (sodium, potassium, magnesium, phosphate, total protein, chloride, bicarbonate, calcium, BUN, creatinine, uric acid, total bilirubin, alkaline phosphatase, AST, ALT, LDH, albumin, and glucose)
- Pregnancy test (women of childbearing potential)
- Collect plasma for biomarker sampling
- Collect plasma for PK sampling on Cycle 4, Day 1 only (2 hours post-dose)
  - CUDC-907 will be administered in the clinic on PK sampling days.
- Update concomitant medications
- Collect AEs
- CUDC-907 dosing (CUDC-907 is taken PO for 5 days on/2 days off)

#### **13.2.2.2. Cycles 2-6, Days 2-5, Days 8-12, Days 15-19**

- CUDC-907 dosing (CUDC-907 is taken PO for 5 days on/2 days off)

### **13.2.3. Cycles 7+**

Note: Subjects who continue past Cycle 13 will only be required to have a Day 1 visit at the beginning of every other cycle (14, 16, 18, etc.).

### **13.2.3.1. Cycles 7+, Day 1**

The following procedures will be performed on Day 1 of Cycles 7+:

- Physical examination
- Update ECOG performance status
- Vital signs (blood pressure, heart rate, respiratory rate, temperature, and weight)
- Lymphoma assessment (includes physical examination, a review of the subject's current signs and symptoms, B symptoms, and concomitant medications)
- Radiologic assessment (CT/MRI [If FDG-PET/CT is acquired at baseline, follow-up FDG-PET/CT imaging at Cycle 10 is required])
- CBC with differentials
- Serum chemistries (sodium, potassium, magnesium, phosphate, total protein, chloride, bicarbonate, calcium, BUN, creatinine, uric acid, total bilirubin, alkaline phosphatase, AST, ALT, LDH, albumin, and glucose)
- Pregnancy test (women of childbearing potential)
- Collect plasma for biomarker sampling
- Update concomitant medications
- Collect AEs
- Collect plasma for PK sampling (2 hours post-dose) every other cycles (i.e., Cycles 6, 8, 10, etc.)
  - CUDC-907 will be administered in the clinic on PK sampling days.
- CUDC-907 dosing (CUDC-907 is taken PO for 5 days on/2 days off)

### **13.2.3.2. Cycles 7+, Days 2-5, Days 8-12, Days 15-19**

- CUDC-907 dosing (CUDC-907 is taken PO for 5 days on/2 days off)

### **13.2.4. End of Therapy Visit (Day 30)**

The following procedures will be performed at the EOT visit:

- Physical examination
- Update ECOG performance status
- Vital signs (blood pressure, heart rate, respiratory rate, temperature, and weight)
- ECG
- Pregnancy test (women of childbearing potential)
  - A serum or urine pregnancy test will be performed at the EOT visit, as well as during Screening and at least once per cycle prior to dosing, or more frequently as clinically indicated.

- Lymphoma assessment (includes physical examination, a review of the subject's current signs and symptoms, B symptoms, and concomitant medications)
  - Done only if not performed within 4 weeks of the EOT visit
- Radiologic assessment (CT/MRI)
  - Done only if not performed within 4 weeks of the EOT visit
- CBC with differentials
- Serum chemistries (sodium, potassium, magnesium, phosphate, total protein, chloride, bicarbonate, calcium, BUN, creatinine, uric acid, total bilirubin, alkaline phosphatase, AST, ALT, LDH, albumin, and glucose)
- Update concomitant medications
- Collect AEs

### **13.3. Post-Treatment Follow-up Visits**

#### **13.3.1. Follow-up Visits $\leq$ 6 Months (Every 12 Weeks)**

- Symptom-directed physical examination (performed until time of disease progression, withdrawal of consent, or any other criteria that would make the subject unable to be followed for disease response)
- IPI score
- Lymphoma assessment (includes physical examination, a review of the subject's current signs and symptoms, B symptoms, and concomitant medications)
- Radiologic assessment (CT/MRI)
- Survival status
- Update concomitant medications (anti-cancer therapies only)
- Collect AEs (only treatment-related SAEs will be captured)

#### **13.3.2. Follow-up Visits $>$ 6 Months (Every 24 Weeks)**

- Symptom-directed physical examination (performed until time of disease progression, withdrawal of consent, or any other criteria that would make the subject unable to be followed for disease response) and updated
- IPI score
- Lymphoma assessment (includes physical examination, a review of the subject's current signs and symptoms, B symptoms, and concomitant medications)
- Radiologic assessment (CT/MRI)
- Survival status
- Update concomitant medications (anti-cancer therapies only)

- Collect AEs (only treatment-related SAEs will be captured)

## 14. STATISTICAL ANALYSES

### 14.1. Overview of Study Design

The safety and preliminary efficacy of CUDC-907 will be evaluated when administered in subjects with RR MYC-altered DLBCL. Patients with RR DLBCL will be tested for MYC-altered disease, defined as *MYC* translocation by FISH, or MYC expression in  $\geq 40\%$  of tumor cells by IHC staining and/or *MYC* gene copy number gain by FISH based on fresh or archived tumor tissue sample (most recent available).

Based on central testing and review, subjects will be classified into one of the following categories: (1) Group A: *MYC* translocation+ by FISH, (2) Group B: MYC expression in  $\geq 40\%$  of tumor cells by IHC and/or *MYC* gene copy number gain by FISH, or (3) Group C: *MYC* translocation by FISH and MYC expression in  $< 40\%$  of tumor cells and no *MYC* gene copy number gain by FISH.

Subjects in all groups will continue to receive treatment until they meet criteria for treatment discontinuation.

### 14.2. Study Endpoints

#### 14.2.1. Primary Endpoint

- ORR (central determination)

#### 14.2.2. Secondary Endpoints

- ORR (local determination)
- PFS, median PFS, and PFS6 (central and local determination)
- OS
- DCR and DOR (central and local determination)
- To evaluate the incidence and severity of AEs, SAEs, and other safety parameters in subjects receiving CUDC-907.
- To characterize the PK of CUDC-907.

#### 14.2.3. Exploratory Endpoints

- To explore the effects of CUDC-907 on disease-associated biomarkers.
- To explore the relationship between disease-associated biomarkers in plasma and tumor tissue. Among biomarkers of interest, BCL2 and BCL6 protein expression and translocation status in particular will be tested in tumor tissue, where possible.
- To explore biomarkers of response for patient selection.
- To explore the relationship between additional biomarkers and biomarker profiles that may influence biologic and clinical responses to CUDC-907.

- To explore the ORR according to Lugano classification ([Cheson et al, 2014](#); [Barrington et al, 2014](#)).

### 14.3. Sample Size Considerations

The sample size for Groups A and B was determined based on the following:

With a sample size of 50 subjects in Groups A and B with an ORR of 30.0%, a two-sided 95% confidence interval employing the exact binomial method will extend from 17.9% to 44.6%. This confidence bound (CB) about the observed ORR is thought to adequately characterize the disease response of these populations after receiving CUDC-907.

Below are the 95% confidence intervals for various response rates using a sample size of 50 subjects and employing the exact binomial methodology.

Sample Size	ORR	Lower 95% Confidence Bound	Upper 95% Confidence Bound
50	15 (30%)	17.9%	44.6%
50	14 (28%)	16.2%	42.5%
50	13 (26%)	14.6%	40.4%
50	12 (24%)	13.1%	38.2%

Enrollment within a group or overall may also terminate early due to other considerations such as those that may preclude timely completion of the study (e.g., low prevalence of MYC-altered DLBCL).

### 14.4. Statistical Analysis

The statistical analyses will be performed using SAS® version 9.4 or later (SAS Institute Inc., Cary, NC). A comprehensive statistical analysis plan (SAP) will be finalized prior to database lock.

#### 14.4.1. Analysis Populations

The Intent-to-Treat (ITT) Population will consist of all subjects in Groups A and B. The primary analyses of efficacy will be conducted based on the ITT Population.

The Evaluable Population will consist of all subjects in Groups A and B who receive at least one full cycle of treatment and have at least one post-baseline disease assessment and have not had major protocol deviations that are thought to have materially impacted efficacy outcomes. Major protocol deviations will be identified prior to database lock. Secondary analysis of efficacy will also be conducted based on the Evaluable Population. In addition, the primary efficacy endpoint (ORR) will also be assessed using the Evaluable Population as a secondary analysis.

The Safety Population will consist of all subjects who receive any treatment. All safety analyses will be conducted based on this population.

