**Statistical Considerations:**

Efficacy Endpoints:

The primary efficacy endpoint is ORR as determined by the central determination of disease response. Secondary endpoints include ORR as determined by the investigative site, and PFS, median PFS, PFS6, OS, DCR, and DOR as determined by both the central determination of disease response and investigator site. An exploratory efficacy endpoint will assess ORR (CR, PR) according to Lugano classification ([Cheson et al, 2014](#); [Barrington et al, 2014](#)).

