**Statistical Considerations (Continued):**

Analysis Populations Evaluable for Safety and Efficacy:

The Intent-to-Treat (ITT) Population will consist of all subjects assigned to Groups A and B. The primary analyses of efficacy will be conducted based on the ITT Population.

The Evaluable Population will consist of all subjects in Groups A and B who receive at least one full cycle of treatment and have at least one post-baseline disease assessment and have not had major protocol deviations that are thought to have materially impacted efficacy outcomes. Major protocol deviations will be identified prior to database lock. Secondary analyses of efficacy will also be conducted based on the Evaluable Population. In addition, the primary efficacy endpoint (ORR) will also be assessed using the Evaluable Population as a secondary analysis.

The Safety Population will consist of all subjects who receive any study treatment. All safety analyses will be conducted based on this population.

Sample Size Determination:

The sample size for Groups A and B was determined based on the following:

With a sample size of 50 subjects in Groups A and B with an ORR of 30.0%, a two-sided 95% confidence interval employing the exact binomial method will extend from 17.9% to 44.6%.

This confidence bound (CB) about the observed ORR is thought to adequately characterize the disease response of these populations after receiving CUDC-907.

Interim Analyses:

- Interim analyses of efficacy using the Evaluable Population will be performed after ORR has been determined in 25 evaluable subjects for both Groups A and B, separately. In both Groups A and B, the ORR using the local determination of disease response will be obtained. If the lower bound of a single-sided 95% confidence interval using the exact binomial method is less than 10% (i.e., 5 responses or less out of 25 patients) in either group, enrollment in that group will not continue.

Efficacy Analyses:

The primary analyses of efficacy will be conducted based on the ITT Population and the interim analyses will be performed on the Evaluable Population. However, secondary analyses will be performed on the ITT and Evaluable Populations. The primary efficacy endpoint, ORR, will be based on the proportion of subjects with CR or PR using the central determination of disease response in both Groups A and B, separately. The estimate will be accompanied by a two-sided exact binomial 95% CB.

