Progression-free survival, OS, and DOR will be summarized descriptively using the Kaplan-Meier method.

Progression-free survival, median PFS, and PFS6 based on the Kaplan-Meier analyses will be reported. For OS, the estimated rates at 3, 6, 9 and 12 months based on the Kaplan-Meier analyses will be reported. For duration of objective response, the estimate of the median based on the Kaplan-Meier analyses will be reported. Waterfall plots will be used to depict graphically the maximum decrease from baseline in the sum of the product diameters in measurable nodes and nodal masses. Secondary analyses of efficacy will be conducted based on the Evaluable Population. The estimate will be accompanied by a two-sided exact binomial 95% lower CB.

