### 6.1.1. Relapsed/Refractory MYC-Altered Diffuse Large B-Cell Lymphoma

#### 6.1.1.1. Diffuse Large B-Cell Lymphoma

Diffuse large B-cell lymphoma (DLBCL), a biologically aggressive type of non-Hodgkin lymphoma (NHL) that arises from B cells, is the most common form of NHL in the United States (U.S.) and Europe. DLBCL meets requirements for orphan disease status in the U.S. and Europe, with a prevalence of less than 200,000 persons in the U.S. and fewer than 5 persons per 10,000, respectively (Howlader et al, 2014; Bray et al, 2013). The U.S. Food and Drug Administration (FDA) granted CUDC-907 orphan drug status for this disease on April 2, 2015.

DLBCL is a heterogeneous disease. While subtypes differ in prognosis and response to treatment, the disease is rapidly fatal if untreated. Clinically, patients with DLBCL usually present with advanced and often extranodal disease. DLBCL can be primary (arising *de novo*) or secondary (representing progression or transformation of a less aggressive lymphoma, such as follicular lymphoma). Since approval of rituximab for the treatment of DLBCL, this agent has become an integral part of various cytotoxic standards of care, including R-CHOP (rituximab, cyclophosphamide, doxorubicin, vincristine, and prednisone). While R-CHOP is commonly used in 1st line treatment, a considerable proportion of patients with advanced stage disease and certain adverse clinical risk factors are not cured with this or other standard therapies (Friedberg and Fisher, 2008). Approximately 40% of patients have refractory disease or disease that relapses after initial response and most patients with relapsed DLBCL ultimately succumb to the disease (Sehn, 2012). Based on systematic review of the literature focused on interventions for relapsed and/or refractory (RR) DLBCL, median progression-free survival (PFS) ranges from 1 - 10 months and median overall survival (OS) ranges from 4 to 13 months (Colosia et al, 2014).

The prognosis for subjects with DLBCL has long been considered to be dependent on risk factors such as those measured by the International Prognostic Index (IPI). The IPI assigns patients to 1 of 4 risk category groups on the basis of 4 factors (i.e., age > 60, stage III or IV

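### The plan appears to extend OS and PFS to the Evaluable Population, whose entry rule removes early deaths, so Evaluable OS from first dose would be biased upward relative to ITT

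*Combined protocol and SAP*

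**What the plan says.** Section 14.4.1 makes ITT, meaning all subjects in Groups A and B, the main efficacy set: "The primary analyses of efficacy will be conducted based on the ITT Population". The Evaluable Population is the part of Groups A and B who "receive at least one full cycle of treatment and have at least one post-baseline disease assessment" and have no major protocol deviation thought to have affected efficacy.

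The same section then states: "Secondary analysis of efficacy will also be conducted based on the Evaluable Population". A separate sentence follows: "In addition, the primary efficacy endpoint (ORR) will also be assessed using the Evaluable Population as a secondary analysis". The Synopsis (Statistical Considerations) has the same pair of sentences. Under Efficacy Analyses it adds that "secondary analyses will be performed on the ITT and Evaluable Populations", and it closes the Kaplan-Meier and waterfall-plot text with "Secondary analyses of efficacy will be conducted based on the Evaluable Population".

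The Synopsis defines what is secondary: "Secondary endpoints include ORR as determined by the investigative site, and PFS, median PFS, PFS6, OS, DCR, and DOR". Section 14.2.2 lists the same efficacy endpoints. Section 14.4.3 plans Kaplan-Meier OS rates at 3, 6, 9 and 12 months, and PFS6. It describes no landmark or delayed-entry method for the Evaluable set.

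**The concern.** Membership of the Evaluable Population depends on surviving long enough to qualify. If OS is timed from first dose in that set, subjects who die before qualifying disappear from the numerator and denominator, and those who remain cannot have an event in the qualifying interval. Later Kaplan-Meier estimates are then too high relative to ITT, with no treatment effect needed.

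The interval is not trivial in this disease. Section 6.1.1.1 calls it rapidly fatal if untreated and cites a review in which median PFS "ranges from 1 - 10 months and median overall survival (OS) ranges from 4 to 13 months". In a single-arm trial no concurrent control would show the inflation, and two OS curves per group leave room to quote the higher one.

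**Working it through.** **1. Do OS and PFS reach the Evaluable set?** Section 14.4.1 sends secondary efficacy analysis to the Evaluable Population and then adds ORR in its own sentence. If the first sentence covered ORR alone, the second would be redundant. The Synopsis sends secondary analyses to both populations, and PFS, PFS6 and OS are secondary efficacy endpoints there and in Section 14.2.2. On the other side, Section 14.4.3 details only ORR for these analyses, with an exact binomial bound. Inclusion of survival is therefore the natural reading, but an inference.

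**2. How early can a subject qualify?**
- Full cycle: 21 days (Section 10.5.1).
- First scheduled scan: Days 15 to 21 of Cycle 2, ± 3 days (Sections 5.1, footnote 9, and 11.3.2). In study days, 21 + 15 = 36 and 21 + 21 = 42, so the window is Day 33 to 45, with midpoint 39.
- End-of-therapy scan: due 30 ± 7 days after the last dose if none was done within 4 weeks (Section 5.1). A subject who stops after the last Cycle 1 dose on Day 19 would reach it at about Day 42 to 56. This route recovers subjects who stop treatment, not those who die early.
- Unscheduled scan: possible at any time. Disease assessment is not defined as a scan, so on a loose reading the lymphoma assessment on Cycle 2 Day 1 (Section 11.2.5), about Day 22, could also count.

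The full-cycle rule alone is thus the lower case, and the Cycle 2 scan at Day 39 the upper case.

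**3. Size for OS.** The plan gives no figure for early loss, so there is none to reproduce. Assumptions: exponential OS from Cycle 1 Day 1; medians of 4 and 13 months (Section 6.1.1.1); 30.4375 days per month; entry requires being alive at L.

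- S(t) = 0.5^(t/median)
- Excluded = 1 − S(L)
- Evaluable S(t) = S(t)/S(L), for t > L

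L = 21 days = 0.690 months; L = 39 days = 1.281 months.

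| Median OS | L | S(L) | Excluded | 3-month OS, ITT → Evaluable | Gain |
|---|---|---|---|---|---|
| 4 months | 21 d | 0.887 | 11.3% | 59.5% → 67.0% | 7.5 points |
| 13 months | 21 d | 0.964 | 3.6% | 85.2% → 88.4% | 3.2 points |
| 4 months | 39 d | 0.801 | 19.9% | 59.5% → 74.2% | 14.8 points |
| 13 months | 39 d | 0.934 | 6.6% | 85.2% → 91.2% | 6.0 points |

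Moving the scan across Day 33 to 45 gives 3-month OS of 72% to 77% (median 4 months) or 90% to 92% (median 13 months). At 6 months with L = 39 days, 35.4% becomes 0.354/0.801 = 44.1%, and 72.6% becomes 0.726/0.934 = 77.8%. Under this model the median rises by L itself, 0.7 or 1.3 months.

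A simulation of 20,000 groups of 50 with entry at Day 42 gave 3-month OS of 59.4% → 75.5% (median 4) and 85.2% → 91.7% (median 13). The formula gives 75.5% and 91.7%.

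**4. PFS.** Progression first seen on a qualifying scan stays in the set; deaths before qualifying do not. If only those deaths are lost, Evaluable PFS6 = PFS6/S_OS(L). Pairing the ends of the background ranges (an assumption) at L = 39 days:
- PFS median 10 months, OS median 13: 66.0% → 0.660/0.934 = 70.6%.
- PFS median 1 month, OS median 4: 1.6% → 0.0156/0.801 = 2.0%.

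These are illustrations. The result also depends on how subjects who stop unscanned are censored, which Section 14.4.3 leaves to a cited guidance.

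**The case against.** The strongest reply is that no sentence assigns OS or PFS to the Evaluable Population. Section 14.4.3 ties these analyses to response by central and site determination, names ORR, and attaches an exact binomial bound. In the Synopsis, too, the sentence after the Evaluable one refers to such a bound. That language fits a proportion, not a survival curve, and Section 14.4 defers detail to a SAP finalised before database lock. This stands as a limit on certainty. It does not remove the point, because Section 14.4.1 and the Synopsis would lead a programmer to produce the survival tables.

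Several stronger readings are tempting, and the documents do not support them:
- A reader might infer that entry is possible only through a scan near week 6. Disease assessment is undefined and other scans could count, so the Day 39 figures are an upper case. The full-cycle rule is mandatory and gives the smaller one.
- A reader might infer that Evaluable PFS6 must be inflated as clearly as OS. Progression on a qualifying scan is kept. If subjects who stop unscanned are censored at baseline in ITT, dropping them changes little.
- A reader might infer that Evaluable survival will be set against historical figures that include early deaths. The documents plan no such comparison, summarise survival descriptively, and do not say how the cited review treated early deaths.

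It is also fair that ITT is primary, that secondary analyses are run in ITT too, and that the interim rule (Section 14.4.3.1) uses ORR. No decision rests on Evaluable survival.

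**Conclusion.** The point holds as a defect in supportive analyses. Read naturally, the plan produces Evaluable OS and PFS curves without correcting for an entry rule that depends on early survival. The upward direction for OS timed from first dose, relative to ITT, needs no survival model. It needs only that some deaths precede qualification.

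The size does rest on a model: exponential OS, and background medians for relapsed or refractory DLBCL in general rather than data from this trial. On that basis the full-cycle rule alone excludes about 4% to 11% of subjects and adds about 3 to 7.5 points to 3-month OS. Requiring the Cycle 2 scan at Day 39 excludes about 7% to 20% and adds up to about 6 to 15 points. The PFS bias is smaller and its extent uncertain.

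A reader might conclude that the trial's main efficacy result is compromised. It is not: the ITT analyses, the primary endpoint and the interim rule are untouched by this point.

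**What to change.** In the Synopsis (Analysis Populations and Efficacy Analyses), Section 14.4.1 and Section 14.4.3, state that PFS, median PFS, PFS6 and OS are estimated in the ITT Population only. If an Evaluable survival curve is kept, start its clock at the qualifying assessment, label it a landmark analysis, and define which assessments qualify.

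Evaluable ORR and DCR can remain as supportive analyses, with a note that early deaths leave their denominators too, so they share the upward tendency.

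The change needs wording only and no new data. It costs some supportive tables, and the supportive survival figures will look less favourable.
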